## STUDY DIAGRAM

## 1 BACKGROUND INFORMATION AND RATIONALE

### 1.1 Introduction

Improving diversity in research projects and national data repositories is critical to providing safe and effective care to marginalized groups. Unfortunately, certain groups, such as African Americans, are inadequately represented in much of the available data and in current clinical trials. Recently, investigators have begun employing new messaging approaches to increase diversity in clinical trial enrollment. These messages are typically designed to inform, with no appeal for specific groups to act. Very little is known about the potential impact of inclusion appeals--direct appeals to historically marginalized groups calling on their need to be included in research studies. Applying the science of appeals to recruitment messages may improve the effectiveness of educational videos and lead to greater participation in research. This pilot study proposes to empirically study whether an inclusion appeal increases attempts to enroll children in studies.

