planning to invite participants to complete the study at a Penn or CHOP facility, rather than at home. Study participants will complete materials using an online survey completion and video display system (REDCap or Qualtrics). Each participant will complete questions about their age, gender identity, race/ethnicity, education attainment, and their child's age and gender identity. We will then ask a subset of questions from the NIH Health Information National Trends Survey to assess clinical trials knowledge. After these questions, all eligible participants will be randomly show either one of two videos (with or without the inclusion appeal) followed by a short survey about perceived effectiveness of the message or taken directly to the final question. The final question will ask if they are willing to receive messages about potential clinical trials for their child. If they select yes, they will be taken to the enrollment screen for the registry above and will be given assistance by the research coordinator to help them complete the process if required.

Each participant will be paid \$20 for participating in the study. The primary outcome will be intention to join a research registry called the Research Discovery Finder that notifies parents about research studies. We will measure attempts to join, rather than joining, in case the process of joining is too complicated or confusing. Based on data from two similar studies in adults we will need approximately 30 completed surveys per group to have 80% power to detect a difference with a 0.05 significance level. Results will be reported using standard descriptive statistics. Between group differences in intent to enroll will be analyzed using chi-square analysis, with significance set at the 0.05 level. We will use a series of one-way between-group analyses of variance to determine the impact of the experimental video on dependent variables.

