# **5 STATISTICAL CONSIDERATIONS**

## **5.1 Primary Endpoint**

The primary endpoint will be the difference in intent to enroll between the three groups.

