## **5.2 Secondary Endpoints**

A secondary endpoints will be the difference in message effectiveness between the video with versus without the inclusion appeal, evaluated using a 6-question survey adopted from KC Davis and colleagues.

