## **5.4 Sample Size and Power**

Based on data from two similar studies in adults we will need approximately 20 completed surveys per group to have 80% power to detect a difference with a 0.05 significance level. Because our plan is to conduct the study before or after scheduled clinic visits, where illness, weather and transportation may impact a family's ability to complete the study, we plan to enroll 90 patients to account for this attrition.

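### The planned tests give neither the size nor the direction of the appeal effect, and no confidence interval is planned for the comparison named in the primary objective

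*Combined protocol and SAP*

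**What the plan says.** **Question.** The introduction (section 1.1) asks something directional: "This pilot study proposes to empirically study whether an inclusion appeal increases attempts to enroll children in studies". Section 2.1 makes the primary objective a two-arm contrast, the appeal video against the no-appeal video, on intent to enroll.

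**Endpoints.** Section 5.1 states: "The primary endpoint will be the difference in intent to enroll between the three groups". Section 5.2 gives the secondary endpoint as "the difference in message effectiveness between the video with versus without the inclusion appeal".

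**Analysis.** Section 3.1.1 promises standard descriptive statistics and then a test: "Between group differences in intent to enroll will be analyzed using chi-square analysis, with significance set at the 0.05 level". It adds a series of one-way analyses of variance. Section 5.3.2 names only the analyses of variance for enrolment intent across the three groups. The 0.05 level is tied to the intent test alone; section 5.2 gives no test or threshold for message effectiveness.

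**Size.** Section 3.1.1 says "we will need approximately 30 completed surveys per group to have 80% power to detect a difference with a 0.05 significance level"; section 5.4 says "we will need approximately 20 completed surveys per group to have 80% power to detect a difference with a 0.05 significance level". Neither gives the difference or the rates behind the figure; 5.4 says only "Based on data from two similar studies in adults".

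No section names a risk difference, ratio or mean difference as a result to be reported, plans a confidence interval, or says how a non-significant result will be interpreted.

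**The concern.** The objective asks whether the appeal raises intent and, implicitly, by how much. A three-group chi-square or F statistic asks only whether the arms differ somewhere. A small p-value could come from either video against the short description, and a large one does not show what the data exclude. A pilot should hand a later trial a range of plausible appeal effects, and the stated inference does not produce one. With 20 to 30 people per arm that range is wide, so the gap between not significant and no worthwhile effect is large.

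**Working it through.** **Inputs.** From the documents: three arms; significance level 0.05; 80% power; 30 per group (3.1.1) or 20 per group (5.4); about 90 evaluable (3.1.4), which is 90 / 3 = 30 per arm if allocation is equal. Not in the documents and assumed here: two-sided testing, equal allocation, and comparator intent rates, shown over a range.

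**1. The plan's own figure.** Without rates or a target difference, neither 30 nor 20 per group can be reproduced. The two figures also cannot share one effect. If 30 per group gives 80%, then 20 gives about Φ((1.960 + 0.842) × √(20/30) - 1.960) = Φ(0.33) = 63%. If 20 gives 80%, then 30 gives about Φ(2.802 × √(30/20) - 1.960) = Φ(1.47) = 93%.

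**2. Direction.** Take illustrative yes-counts of 9, 9 and 20 out of 30. The pooled rate is 38/90 = 0.422 and the expected count is 12.67 per arm. Chi-square = (3.67² + 3.67² + 7.33²) / (30 × 0.422 × 0.578) = 80.7 / 7.32 = 11.0 on 2 df, p = 0.004. The p-value is the same whether the 20 falls in the appeal, no-appeal or no-video arm.

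**3. Difference needed for 80% power, appeal versus no-appeal.** Power = Φ((d - 1.96 × √(2p̄(1 - p̄)/n)) / √((p1(1 - p1) + p2(1 - p2))/n)), where p1 is the comparator rate, p2 = p1 + d and p̄ is their mean. For example, with n = 30, p1 = 0.30 and d = 0.355: (0.355 - 0.253) / 0.121 = 0.85, so power is 80%.

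| Comparator rate | Points needed, 30 per arm | Points needed, 20 per arm |
|---|---|---|
| 10% | 30.9 | 39.3 |
| 20% | 34.3 | 42.4 |
| 30% | 35.5 | 43.0 |
| 40% | 35.1 | 42.0 |
| 50% | 33.5 | 39.6 |
| 60% | 30.6 | 35.8 |
| 70% | 26.5 | not reached |

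By the same formula, a true 20-point difference has 34% to 49% power at 30 per arm and 24% to 35% at 20. The overall 2-df chi-square does no better: for rates of 30%, 30% and 50% its power is 36% at 30 per arm and 25% at 20.

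**4. What an interval would show.** Take 15/30 without and 21/30 with the appeal. The pooled rate is 0.60, so chi-square = 0.20² / (2 × 0.60 × 0.40 / 30) = 0.04 / 0.016 = 2.5 and p = 0.11. The Wilson limits are 0.332 to 0.668 and 0.521 to 0.833. Newcombe's method combines them:

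- lower: 0.20 - √((0.700 - 0.521)² + (0.668 - 0.500)²) = 0.20 - 0.246 = -0.046
- upper: 0.20 + √((0.833 - 0.700)² + (0.500 - 0.332)²) = 0.20 + 0.215 = +0.415

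| Observed (no appeal vs appeal) | Difference | 95% Newcombe interval, points | p |
|---|---|---|---|
| 15/30 vs 21/30 | +20 | -5 to +41 | 0.11 |
| 15/30 vs 15/30 | 0 | -24 to +24 | 1.00 |
| 10/20 vs 14/20 | +20 | -10 to +45 | 0.20 |

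The first two rows are both non-significant, yet they say quite different things about the appeal. The p-value against 0.05 does not convey this; the interval does.

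**The case against.** **Descriptive statistics are planned.** This stands in part. Per-arm percentages for a yes/no outcome would show direction and size, and a reader could compute an interval from the counts. So the plan does not rest on p-values alone. It still does not commit to an estimate of the appeal contrast with its uncertainty, or to basing the conclusion on it.

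**The trial may well reach significance.** This stands. A reader might infer that the study will most likely end in a null result. The documents do not support that, because they give no true effect. By exact enumeration at 30 per arm, power for a 25-point difference is 51% to 78% (comparator 10% to 70%), and for 35 points it is 80% to 89% (comparator 10% to 50%).

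**Nothing says that p above 0.05 will be read as no effect.** This also stands. A reader might infer such a rule from the 0.05 cut-off, but no section states one. Section 1.4, in reporting an earlier educational-video trial with no effect, adds that only half the participants watched the video. That is a qualified reading of a null result.

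**Twenty per arm is a low case.** Fair. Section 5.4 gives 20 as the completed surveys needed while saying "we plan to enroll 90 patients to account for this attrition", and section 3.1.4 expects 90 evaluable. The point holds at 30.

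**An interval adds no power, and a two-video primary result is narrower than section 5.1.** Both are true. The interval only shows what the data rule out. The narrower contrast is the one that section 2.1 names.

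**Conclusion.** The point holds as a mismatch between the primary objective and the stated inference. The objective is a two-arm contrast; the inference is a three-group chi-square, or analyses of variance, without an interval. Section 3.1.1 could be read as intending pairwise chi-square tests. Each would then address one pair of arms, but its p-value would still carry no size or interval.

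At 30 per arm, 80% power needs a true difference of about 27 to 36 points (comparator 10% to 70%). At 20 per arm it needs about 36 to 43 points (comparator 10% to 60%). These figures assume two-sided 0.05 and equal arms. A non-significant result would therefore not by itself exclude a worthwhile effect. How much it excludes depends on the data: even identical observed rates of 50% at 30 per arm leave -24 to +24 points open. The need for an estimate and interval does not depend on the assumed rates. The trial can run as designed; the change should be made before the data are analysed.

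**What to change.** - **Sections 3.1.1 and 5.3.2:** make the primary result the difference in the proportion answering yes, appeal minus no-appeal video, with a 95% Newcombe interval. Keep the three-group chi-square p-value as supporting information and reconcile it with the analyses of variance now named for the same outcome. State that the conclusion rests on the interval.
- **Section 5.1:** align the endpoint sentence with the two-video contrast in section 2.1, with the no-video comparisons as supporting.
- **Section 5.2:** report the mean difference in the effectiveness score between the two videos with a 95% confidence interval.

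The cost is a few lines of protocol text and a line or so of R, which section 7.2 already names as analysis software. No participants, data or visits are added. The downside is that a wide interval is shown openly. The 20 versus 30 per group conflict and the unstated target difference need their own correction; an interval does not repair them.

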### **3.1.2 Allocation to Treatment Groups and Blinding**

n/a

### **3.1.3 Study Duration, Enrollment and Number of Sites**

The study duration per subject will be approximately 6 months for Phase 1 parents, and one visit for Phase 2 (including screening), with no planned follow-up.

### **3.1.4 Total Number of Study Sites/Total Number of Subjects Projected**

The study will be conducted at one site in the Philadelphia area.

It is expected that approximately 100 subjects will be enrolled to produce 90 evaluable subjects. The study enrollment is planned to conclude in October 2022.

## **3.2 Study Population**

Subjects that do not meet all of the below enrollment criteria may not be enrolled. Any violations of these criteria must be reported in accordance with IRB Policies and Procedures.

### **3.2.1 Inclusion Criteria**

- English speaking (Phase 1 and 2)
- Self-identified African or African American (Phase 2 only)
- Not already enrolled in registry, no history of clinical trial participation (Phase 2 only)
- At least one child in their care age newborn to 13 (Phase 2 only)

### **3.2.2 Index/Case Subject Exclusion Criteria**

- Parents under the age of 18
- Parents with all children over the age of 13
- Non-English speakers
- Previously enrolled in CHOP's registry, history of clinical trial participation

### **3.2.3 Control Subject Inclusion Criteria**

Same as 3.2.1

### **3.2.4 Control Subject Exclusion Criteria**

Same as 3.2.2

## **4 STUDY PROCEDURES**

### **4.1 Visit 1 (Phase 1)**

- Welcome and introductions
- Participants will return signed informed consent (mailed to them before the visit.)
- Participants will see a presentation about the goals of the study and be invited to ask questions.
- Participants will see a first version of the video.
- Participants will complete a video effectiveness survey.
- Participants will discuss the video (open-ended, informed by the survey questions)

### **Subsequent Visits (Phase 1, up to three additional visits)**

- Welcome and introduction
- Participants will see a presentation about the goals of the study and summary of how the video has been changed.
- Participants will see a revised version of the video.
- Participants will complete a video effectiveness survey.
- Participants will discuss the video (open-ended, informed by the survey questions)

## **4.1 Visit 1 (Phase 2)**

Detailed description of study visit including all procedures.

Potential participants will be invited to enroll in the study based on scheduled information and self-identified race/ethnicity.

Upon arrival to clinic, potential participants will complete a brief screening form related to the inclusion criteria (English proficiency, able to watch a video or see an image, African/African American race). If inclusion criteria are met, they will receive informed consent form (with review and discussion) and be asked to sign it.

Participants will complete an online survey containing: (1) demographic questions (their age, gender identity, education attainment, and their child's age and gender identity); (2) clinical trials knowledge, using a subset of questions from the NIH Health Information National Trends survey

Participants will be randomly shown either: (1) one of two videos (with or without the inclusion appeal) followed by a short survey about perceived effectiveness of the message; or (2) a paragraph and image describing the CHOP Research Discovery Finder.

Participants will be asked if they are willing to receive messages about potential clinical trials for their child from the CHOP Research Discovery Finder. If they select yes, they will be taken to the enrollment screen for the registry above and will be given assistance by the research coordinator to help them complete the process if required.

Each participant will be paid \$20 for participating in the study.

## **Subject Completion/Withdrawal**

Subjects may withdraw from the study at any time without prejudice to their care. The Investigator or the Sponsor (if applicable) may also withdraw subjects who violate the study plan, or to protect the subject for reasons of safety or for administrative reasons. It will be documented whether or not each subject completes the study.

## **Early Termination Study Visit**

Subjects who withdraw from the study after the study has begun and at least one question has been answered on the survey (out of time, lack of willingness or ability to continue, etc.) will be compensated as if the study had been completed.

## **Safety Evaluation**

n/a

# **5 STATISTICAL CONSIDERATIONS**

## **5.1 Primary Endpoint**

The primary endpoint will be the difference in intent to enroll between the three groups.

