### Objectives:

This study will assess whether video-based inclusion appeals improve African American children's enrollment into the Children's Hospital of Philadelphia (CHOP) research study registry.

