### 2.1 Primary Objective (or Aim)

The primary objective is to compare intent to enroll in a research discovery site after seeing a video with an inclusion appeal versus one without such an appeal—focusing on parents and guardians who identify as African or African American.

---

 Jeannine S. Skinner et al., “The Impact of an Educational Video on Clinical Trial Enrollment and Knowledge in Ethnic Minorities: A Randomized Control Trial,” *Frontiers in Public Health* 7 (2019): 104, <https://doi.org/10.3389/fpubh.2019.00104>.

 Joseph Petraglia, “The Importance of Being Authentic: Persuasion, Narration, and Dialogue in Health Communication and Education,” *Health Communication* 24, no. 2 (March 2009): 176–85, <https://doi.org/10.1080/10410230802676771>.

 Melanie B. Tannenbaum et al., “Appealing to Fear: A Meta-Analysis of Fear Appeal Effectiveness and Theories,” *Psychological Bulletin* 141, no. 6 (November 2015): 1178–1204, <https://doi.org/10.1037/a0039729>.

 Graton Aurélien and Mailliez Melody, “A Theory of Guilt Appeals: A Review Showing the Importance of Investigating Cognitive Processes as Mediators between Emotion and Behavior,” *Behavioral Sciences (Basel, Switzerland)* 9, no. 12 (November 20, 2019): E117, <https://doi.org/10.3390/bs9120117>.

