### **5.3.2 Efficacy Analysis**

For our assessment of differences between the three groups' intent to enroll, we will use a series of one-way between-group analyses of variance to determine the impact of the experimental video vs. control video vs. no video on enrollment intent.

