## **7 STUDY ADMINISTRATION**

### **7.1 Treatment Assignment Methods**

#### **7.1.1 Randomizations**

One of three arms will be randomly presented to each participant through a specialized survey flow. Participants will then be administered one of three arms through a web-based randomizer. This data will be recorded and stored in Qualtrics.

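### The primary test compares all three arms, but the primary objective is appeal video versus no-appeal video, so the trial can be positive when the appeal does nothing

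*Combined protocol and SAP*

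**What the plan says.** - **Objective.** Section 2.1 plans to "compare intent to enroll in a research discovery site after seeing a video with an inclusion appeal versus one without such an appeal". The abstract agrees: "This study will assess whether video-based inclusion appeals improve" enrollment in the registry.
- **Endpoint.** Section 5.1: "The primary endpoint will be the difference in intent to enroll between the three groups".
- **Test, section 5.3.2.** "we will use a series of one-way between-group analyses of variance to determine the impact of the experimental video vs. control video", with no video as the third group.
- **Test, section 3.1.1.** "Between group differences in intent to enroll will be analyzed using chi-square analysis, with significance set at the 0.05 level". The groups to be compared are not named. A series of ANOVAs on unspecified dependent variables follows.
- **Arms.** Section 7.1.1: "One of three arms will be randomly presented to each participant". The allocation ratio is not given.
- **Sample size.** Section 3.1.1 gives about 30 completed surveys per group and section 5.4 about 20. Both claim 80% power at 0.05 for a difference that is not specified.

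The only appeal versus no-appeal comparison named in section 5 is the secondary endpoint of message effectiveness (5.2), which is not intent. No section ranks the comparisons of intent or adjusts for their number.

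**The concern.** The two videos differ only by the added appeal segment (sections 1.2 and 3.1.1), so the effect of the appeal is the difference between those two arms. The third arm gets a paragraph and an image. A three-group test combines the effect of the appeal with the effect of showing any video. If video alone raises intent, the primary endpoint as written is met with a useless appeal, and the result could be reported as support for the appeal.

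The reverse risk is a power claim that holds for the three-group test while the question in section 2.1 is badly underpowered.

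The word 'series' adds a further difficulty. If it means separate pairwise tests of intent, no pair is primary and the 0.05 level is unprotected.

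**Working it through.** **Inputs.** From the documents: three arms, a yes/no answer on intent, 20 or 30 completed surveys per group, and a 0.05 level. Assumed: 1:1:1 allocation, two-sided testing, and every intent rate. The plan's own sample size cannot be reproduced because neither section 3.1.1 nor section 5.4 gives rates or an effect size.

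**Tests.** With n per arm, observed proportions p_i and their mean p̄:

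- Three-group chi-square: X² = n Σ(p_i − p̄)² / [p̄(1 − p̄)], significant above 5.99 (2 df).
- Appeal versus no appeal: X² = n(p_1 − p_2)² / [2q(1 − q)], where q = (p_1 + p_2)/2, significant above 3.84 (1 df).

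**One table as illustration.** Suppose 19, 19 and 9 of 30 say yes (appeal, no appeal, no video). The expected count per arm is 47/3 = 15.67 and p̄ = 47/90 = 0.522. Then X² = (3.33² + 3.33² + 6.67²) / (15.67 × 0.478) = 66.67/7.49 = 8.9. This exceeds 5.99, so the primary result is positive, yet the two videos performed identically.

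**Rejection rates with no appeal effect.** These come from exact enumeration of three binomial arms.

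| Appeal / no appeal / no video | Three-group, n = 30 | Three-group, n = 20 | Appeal vs no appeal, n = 30 | Appeal vs no appeal, n = 20 |
|---|---|---|---|---|
| 50 / 50 / 40% | 11% | 9% | 5% | 4% |
| 50 / 50 / 30% | 35% | 24% | 5% | 4% |
| 60 / 60 / 30% | 68% | 49% | 5% | 5% |
| 65 / 65 / 30% | 82% | 64% | 5% | 5% |

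**Power when the appeal works.** With 70 / 50 / 30% and 30 per arm, the three-group test has 81% power and appeal versus no appeal has 35%. At 20 per arm these are 63% and 25%.

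**If 'series' means three unadjusted pairwise tests.** With all arms equal at 30%, 50% or 70% and 30 per arm, at least one test is significant in 12–13% of trials. Independence would give 1 − 0.95³ = 14.3%.

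**Chi-square or ANOVA.** At equal arm sizes of 20 and 30, the enumeration found no table on which the two three-group tests disagree. The conflict between sections 3.1.1 and 5.3.2 should be tidied, but it does not drive the result. What matters is which arms are compared and how many tests are done.

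**Sample size for the objective's own comparison.** n per arm = [1.96√(2q(1 − q)) + 0.84√(p_1(1 − p_1) + p_2(1 − p_2))]² / (p_1 − p_2)². For 50% vs 70%: (1.96 × 0.693 + 0.84 × 0.678)² / 0.04 ≈ 93. The same formula gives 31 for 30% vs 65%, 42 for 30% vs 60% and 39 for 50% vs 80%, all before attrition.

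**The case against.** **The 'series' may not be pairwise.** Section 3.1.1 uses the same phrase for several dependent variables, which suggests one ANOVA per outcome, and section 5.3.2 lists the three groups together. This is a fair reading, so the 12–13% error rate is conditional on the other one. But on this reading the test of intent is the three-group test, and the main problem remains.

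**A three-group test followed by pairwise tests is safe.** If pairwise tests were done only after a significant three-group result, the overall error with all arms equal would be 4.8–5.2%. A false appeal claim would occur in 2.4–5.0% of trials across the null-appeal scenarios. That is correct, but the plan states no such sequence, and the endpoint in section 5.1 would still be met by the first step alone.

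**The 82% needs a 35-point video effect.** It does, and the background describes mixed results for video messaging. The range of 9% to 82% should be quoted, not the top of it.

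**The no-video arm has a purpose.** Section 2 opens with a broad aim of finding which components of video messages work. That supports keeping the arm and reporting it. It does not make a three-group difference the answer to section 2.1.

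**It is a pilot.** The plan nonetheless names a primary endpoint, a significance level and 80% power, so it should be clear what is being tested.

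**Conclusion.** The concern holds. The primary endpoint and its test do not answer the primary objective. The finding rests on the text and not on the assumed rates: in every scenario examined, a real video effect takes the three-group rejection rate above 5% while the appeal has no effect. Only the size depends on the assumptions, from 9% (50/50/40%, 20 per arm) to 82% (65/65/30%, 30 per arm), under 1:1:1 allocation and two-sided testing. Loss of the 0.05 level is a further consequence only if the ANOVA series is pairwise. This must be corrected, because a positive primary result as now defined cannot be read as evidence for the appeal.

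**What to change.** 1. In sections 5.1 and 5.3.2, name one primary comparison: the proportion answering yes on intent, "after seeing a video with an inclusion appeal versus one without such an appeal", by a two-arm chi-square test at two-sided 0.05, reported as a risk difference with a 95% confidence interval.
2. Make each video versus no video secondary, tested after the primary in a fixed order or with Holm's adjustment. Either is acceptable if stated in advance.
3. Drop the ANOVA series for intent. ANOVA or a t-test can stay for the six-item effectiveness score. Make section 3.1.1 say the same.
4. Restate the sample size for the appeal versus no-appeal pair, with the assumed rates written out, and settle 20 versus 30 per group.

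No arm, visit or data item changes. The real cost is in step 4. The primary comparison uses two of the three arms, and 30 per arm gives about 80% power only for a difference near 30% vs 65%. If the numbers stay as planned, the limited power should be stated openly.

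Section 3.1.4 planned enrollment to end in October 2022. If intent data by arm have already been seen, the amendment should say so and date the change. The choice of comparison is still defensible because it follows the objective already written in section 2.1.
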